2. STUDY OBJECTIVES

Primary objective:

1. **To test if the DUO-EF algorithm can achieve a sensitivity and specificity above 80% for detection of LVEF above or below 40% in comparison to gold-standard echocardiography**

Secondary Objectives:

- To perform a subgroup analysis of DUO-EF against LVEF calculated by cardiac MRI (another gold standard investigation for calculating LVEF <40%)
- To validate consistency of DUO-EF result at point-of-care in GP practice ('real world' use where GP suspects new heart failure) against repeat DUO-EF at time of gold-standard investigation
- To validate consistency of DUO-EF result at point-of-care in Covid-19 follow up clinic ('real world' use where clinicians suspect new heart failure) against repeat DUO-EF at time of gold-standard investigation
- To measure if participants with DUO-EF suggestive of LVEF <40% but with gold standard investigations where LVEF >40% are at increased risk of developing heart failure at 24 months i.e. can DUO-EF predict future development of LVEF <40% at 24 months
- To evaluate DUO-EF point-of-care determination of LVEF<40% in comparison with the components of the established NICE primary care pathway (e.g. BNP result)

3. STUDY DESIGN & METHODS

Statistical Considerations

Type of study: Prospective cross-sectional study comparing identification of LVEF above or below 40% by DUO-EF algorithm versus gold-standard methods.

Duration: Start date 01/02/2021, duration 36 months

Number and type of participants: across all settings 2,400 total

Sample Size

Imperial College Healthcare NHS Trust performs over 20,000 echocardiograms per year across its three hospital and community sites, serving the most ethnically and socioeconomically diverse population in the UK.

Based on established data and extensive clinical expertise of the investigators, around half of all patients who attend for echocardiography at the Trust are found to have LVEF <40%. **The sample size calculation below addresses the primary objective: evaluating if the DUO-EF algorithm can achieve a performance of sensitivity and specificity above 80% for detection of LVEF above or below 40% – compared to gold-standard echocardiography.**

SAMPLE SIZE CALCULATION

Primary Variable: Left Ventricular Ejection Fraction >/< 40%

Null Hypothesis: DUO-EF **DOES NOT** detect with sensitivity and specificity exceeding 80% a LVEF greater or less than 40%

Alternate Hypothesis: DUO-EF **CAN** detect with sensitivity and specificity exceeding 80% a LVEF greater or less than 40%

Type 1 error 5% (5% 2 sided test)

Type 2 error 20% (80% power)

Based on the above parameters for sample size calculation (Ref: G*Power, proportion, difference from a constant [binomial test 1 sample test]) to address the primary objective, this study will recruit participants until at least 500 have been recruited with an LVEF above 40% and 500 with a LVEF below 40% i.e the minimum total required is 1000 patients.

This will provide us with an ability to estimate sensitivity and specificity with a 95% CI $\pm 3.3\%$, and assuming the underlying sensitivity and specificity are at least 85% provide us with 80% power at the 5 % significance level to detect that they exceed the pre-specified criterion of a sensitivity and specificity of 80%.

Dropouts: Dropouts are unlikely within the context of the primary objective since consent and the entire data collection will occur within a short space of time during a single clinical visit (standard-of-care attendance for echocardiography).

Protocol Allowances: Although we require 466 patients with EF >40% and 466 patients with EF <40% we have rounded these up to 500 patients. Furthermore, we will likely need to recruit up to 1,500 patients in total since it is unlikely that the first 1,000 patients will fulfil the exact breakdown of required LVEF above and below 40%.

Controls: The ‘control’ population in this study are participants with LVEF>40%. Indications for referral to echocardiography are broad and include but are not limited to: suspected or known

ischaemic heart disease, suspected cardiomyopathy, pericardial disease, murmurs, assessment of valve disease, assessment of prosthetic valves, assessing chronic lung disease, neurological disease (stroke or transient ischaemic attack), arrhythmia (palpitations and/or loss of consciousness), high blood pressure (common) and as a standard investigation considered before surgery. Many of these referred patients are found to have no abnormalities on echo and are otherwise healthy. Therefore, the unselected approach of this study to include all-comers to echo will generate a population sample that can be evaluated for alignment with the type of population in whom a screening programme for heart failure may be beneficial.

Performance characteristics: Eko Health (the 'manufacturer' of the algorithm) indicate a performance of 80% sensitivity and 80% specificity for the identification of LVEF above or below 40%

Confounders: our study design precludes confounders

Avoidance of bias for primary objective

To avoid any biases in both the recording of DUO-EF readings by the member of the research team and this influencing calculation of %LVEF by the echocardiography team (sonographer), the following steps will be taken:

- The member of the research team approaching patients in the echo department for consent will not be aware of the indication for referral at time-of-consent
- DUO-EF readings can happen before or after the echo, with the member of the research team unaware of the echo-derived %LVEF until they check the electronic health record (after DUO-EF has already been recorded).
- The sonographer will not be made aware of the results of DUO-EF, therefore not biasing any interpretation of %LVEF if borderline around 40%

Study Participant Population

All study participants will be approached to take part and have a DUO-EF reading during the course of their routine care (minimal disruption) in the echo or cardiac MRI setting, during their GP appointment, or while attending COVID-19 follow up clinic. This will result in a large, representative study population to meet the objectives of testing the hypothesis for DUO-EF as a screening tool.

Group 1: Departmental Echocardiography and Cardiac MRI, Imperial College Healthcare NHS Trust

Unselected patients attending for departmental echocardiography (n = 1,500) and subgroup in cardiac MRI (n = 100). Patients will be consented by a member of the research team while they wait for an echocardiogram/cMRI. Patients from group 2 (GP referrals) will also be attending for an echo as part of their routine care on the heart failure pathway; they will be re-consented by a member of the research team upon arrival in the department.

Researchers will perform and record DUO-EF readings on participants and subsequently review echocardiography and cardiac MRI reports and document the LVEF calculated by these modalities.

If echocardiography does not suggest heart failure with LVEF<40% but DUO-EF does, patients will be followed-up with a **24 month phone call** (early evidence indicates the algorithm can identify low ejection fraction before being detectable on echo⁸).

Group 2: Patients in Primary care ('real world' evaluation)

NIHR North West London Primary Care **Clinical Research Network** (n = 10 GP practices). Patients attending GP with signs/symptoms of heart failure (n = 400 in total across all sites) will proceed with standard-of-care NICE heart failure pathway, with no change to standard of care through participation in study. GP's will be asked to record DUO-EF in any patient where heart failure is suspected.

Researchers will capture the point-of-care DUO-EF prediction from the GP:

- Comparing this to repeat DUO-EF ('agreement' between two time points) at time of (group 1) echocardiography (if indicated by standard of care investigations: BNP and 12-lead ECG)
- And comparing both of these DUO-EF measurements to echocardiography derived LVEF

Group 3: COVID-19 Clinic, Imperial College Healthcare NHS Trust

Patients attending COVID-19 follow up clinic (n = 400). Only patients who are being routinely referred onto the heart failure pathway for investigations will be invited to participate i.e. patients **with clinical symptoms of heart failure**, who would/should be referred onto routine NICE pathway. Researchers will capture the point-of-care DUO-EF prediction from the Covid-19 follow up clinic setting:

- Comparing this to repeat DUO-EF ('agreement' between two time points) at time of (group 1) echocardiography
- And comparing point-of-care and time-of-echo DUO-EF results

Method for Single-Lead ECG Collection for DUO-EF

For echo and cMRI, DUO-EF recordings will be made after these gold standard investigations so as not to bias interpretation of results. The protocol for DUO-EF recording for all patients in the COVID-19 follow up clinic, GP, echo and cMRI setting will be as follows:

1. Clinical user turns on Eko DUO device and confirms connection to secure app
2. Participants sitting upright will have 15 second single-lead ECGs recorded by the Eko DUO from five different locations:
 - a. Lead I position (holding the device's electrodes between two hands)
 - b. Clavicle
 - c. Angled
 - d. V2 position
 - e. V5 position
3. Five recordings of DUO-EF recorded by researchers

The participant will be categorised as having a DUO-EF <40% if any of the five DUO-EF readings suggest this.

Data point collection: %LVEF echo, %LVEF cMRI, BNP

Recording %LVEF from echocardiography

EF is routinely measured or estimated using well-established standardized methodologies. For the purpose of this study we draw on previous work by Attia et al (2019) to record the %LVEF value on echocardiography using the first available model in a standard hierarchical sequence:

- EF determined using 3-D echocardiography¹²
- Biplane approach using the Simpson method¹³ a 2-D method, or M-mode
- In the absence of any of the preceding, the reported visually estimated EF

If the estimation is a range, the midpoint as a single LVEF value will be used. LVEF will also be classified as low ($\leq 40\%$), moderately depressed (41–49%), or normal ($\geq 50\%$).

Recording %LVEF from cardiac MRI

As with echo, standard approaches to calculating EF also exist for cMRI. Calculated %LVEF (reported as standard) will be recorded alongside classification as low ($\leq 40\%$), moderately depressed (41–49%), or normal ($\geq 50\%$).

Brain Natriuretic Peptide

Where available, particularly in patients initiated onto the routine diagnostic heart failure pathway in the primary care and COVID-19 follow up clinic setting, BNP will also be recorded by researchers as an additional comparator to DUO-EF. BNP recorded longer than two months before or after DUO-EF will be excluded.

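### The stated 80% power is for each test alone; power for sensitivity and specificity both to exceed 80% is about 68% at the 500 + 500 minimum

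*Protocol*

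**What the plan says.** The primary objective (Protocol, section 2) is "To test if the DUO-EF algorithm can achieve a sensitivity and specificity above 80"% against echocardiography. The null and alternate hypotheses in section 3, Sample Size Calculation, pair the two measures in the same way.

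The same section names a one-sample binomial test against a constant, with 5% two-sided type 1 error and 80% power. Its recruitment rule is that "this study will recruit participants until at least 500 have been recruited with an LVEF above 40% and 500 with a LVEF below 40"%, a minimum of 1,000 in total. Assuming true values of at least 85%, it says this will "provide us with 80% power at the 5 % significance level to detect that they exceed the pre-specified criterion" of 80%.

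Protocol Allowances gives the calculated size before rounding up to 500: "Although we require 466 patients with EF >40% and 466 patients with EF <40"%. It then adds that "we will likely need to recruit up to 1,500 patients in total", because the first 1,000 may not split as needed. The Study Summary and the Group 1 description give the echo cohort as a number: "Unselected patients attending for departmental echocardiography (n = 1,500").

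On prevalence, the Sample Size section states that "around half of all patients who attend for echocardiography at the Trust are found to have LVEF <40"%. On expected performance, the only sensitivity and specificity reported are the manufacturer's, who "indicate a performance of 80% sensitivity and 80% specificity for the identification of LVEF above or below 40"%.

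**The concern.** The objective is met only if two tests succeed, one in patients with low LVEF and one in the rest. A sample size that gives 80% power for each test gives less than that for both. The protocol nevertheless attaches its 80% to the joint claim, at the minimum of 500 + 500.

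If the joint power is well below 80%, a device that truly performs at 85%/85% fails the primary objective more often than the protocol tells its readers, and that failure could be read as a failure of the device. The shortfall also depends on how many patients are enrolled, which the protocol describes both as a rule with a floor (500 per class) and as a planned number (1,500).

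**Working it through.** **Inputs, all from Protocol section 3.** Null value p0 = 0.80; assumed true value p1 = 0.85 for both measures; two-sided 5%, so 0.025 in the upper tail; exact one-sample binomial test.

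**Step 1. Reproduce the protocol's figure.** For each n, take the smallest count r with P(X ≥ r | n, 0.80) ≤ 0.025. Power is then P(X ≥ r | n, 0.85).

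- n = 465: r = 390, power 77.4%
- n = 466: r = 390, upper tail 0.0245, power 80.5%

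So 466 is the first n that reaches 80%, an exact match. A one-sided 5% test would give 365 and does not explain the figure. The 466 is therefore sized for one proportion.

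**Step 2. Power per test at other sizes (true value 85%).**

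| n | r | Power |
|---|---|---|
| 500 | 418 | 82.7% |
| 550 | 459 | 85.8% |
| 600 | 500 | 88.4% |
| 750 | 622 | 94.7% |
| 900 | 744 | 97.6% |
| 1,000 | 825 | 98.7% |

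**Step 3. Joint power.** Sensitivity uses patients with low LVEF and specificity uses the others. Given the class sizes the two tests are independent, so joint power = power(n1) × power(n2).

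| Class sizes | Joint power |
|---|---|
| 466 / 466 | 0.805 × 0.805 = 64.8% |
| 500 / 500 | 0.827 × 0.827 = 68.3% |
| 500 / 550 | 0.827 × 0.858 = 71.0% |
| 500 / 750 | 0.827 × 0.947 = 78.3% |
| 500 / 1,000 | 0.827 × 0.987 = 81.6% |
| 600 / 900 | 0.884 × 0.976 = 86.3% |
| 750 / 750 | 0.947 × 0.947 = 89.7% |

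Over all splits of 1,500 with at least 500 in each class, the range is 79.5% (504/996) to 89.7% (750/750). The low point is not at 500/1,000 because exact binomial power does not rise smoothly with n.

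**Step 4. What each recruitment rule delivers.** If recruitment stops once both classes reach 500, the total follows from the negative binomial distribution. Only the 50% prevalence is the protocol's; the others are assumed.

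| Share with LVEF <40% | Mean total | Mean joint power |
|---|---|---|
| 50% (protocol) | 1,025 | 69% |
| 40% (assumed) | 1,250 | 78% |
| One third (assumed) | 1,500 | 81% |

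If instead 1,500 are always enrolled, joint power at 50% prevalence is 89%.

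**Step 5. Size for 80% joint power.** Each test needs power √0.80 = 89.4%. With equal classes, exact joint power is at least 80% for every n from 630 per class (79.6% at 629). A floor of 630 per class needs about 1,290 patients on average at 50% prevalence.

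**Step 6. The planning value.** If the true values were 80%/80%, each test would succeed with probability at most 0.025, and both with at most 0.025² = 0.06%, at any sample size.

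**The case against.** **The two measures may be meant as separate claims.** The protocol never says outright that both tests must be significant. The outcome section simply lists the two measures, and the sample size section also promises a confidence interval width for each. On that reading 80% per test is correct. However, the objective and both hypotheses join the measures with "and", and the power sentence claims that "they" exceed the criterion. The joint reading is the more natural one, and if separate claims are meant the protocol should say so.

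**The planned 1,500 largely delivers the power.** At 1,500 and 50% prevalence, joint power is 89%, and a floor of 500 per class is compatible with an expected total of up to 1,500. This stands as far as it goes. But the power sentence is attached to the 500 + 500 minimum, and Protocol Allowances treats 1,500 as an upper limit. A literal stop at 500 per class ends near 1,025 patients at the protocol's own prevalence.

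**The 68% applies only at exactly 85%/85%.** At 500 + 500, joint power is 89.1% at 86%/86% and 97.7% at 87%/87%. This is true, but the protocol promises 80% from 85% upward, so 85% is where the promise has to hold.

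**The 85% is openly an assumption.** The protocol does not plan on the manufacturer's 80%/80%, and any test against a threshold rarely succeeds when the truth equals the threshold. That is fair. The missing source for the 85% is a side point and does not carry the finding.

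**Conclusion.** The concern holds. The 466 per class is correct for one test, but the 80% is wrong as a statement about both at the minimum to which it is attached. At 500 + 500 with a true 85%/85%, power is 82.7% per test and 68.3% jointly, so the chance of missing the objective is about 32% rather than 20%. With 1,500 enrolled and at least 500 per class, it is about 80% to 90%.

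This rests on the joint reading of the objective, the two-sided 5% exact test that the protocol names, and true values of exactly 85%. Higher true values raise the power. Requiring both tests to succeed calls for no alpha adjustment; only power is affected. This should be fixed, but it does not threaten the design.

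**What to change.** - **Restate the power sentence**, for example: *At the minimum of 500 + 500 patients and true sensitivity and specificity of 85%, power is about 83% for each and about 68% that both exceed 80%. If 1,500 are enrolled with at least 500 per class, joint power is about 80% to 90%. The primary objective is met only if both tests succeed.*
- **State one recruitment rule**: stop when each class reaches 500, or enrol all 1,500. Use the same rule in the Study Summary, Sample Size Calculation, Protocol Allowances and Group 1 description.
- **If 80% joint power is intended**, enrol the planned 1,500 while keeping the 500-per-class floor, or raise the floor to 630 per class.
- **Give the source of the 85%** and set it against the manufacturer's 80%/80%, noting that at 80%/80% the criterion would almost never be met.

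**Cost.** Wording only, if the lower joint power is accepted. At about 50% prevalence, 80% joint power needs no patients beyond the planned 1,500. At lower prevalence it may: with one third below 40% (assumed), 1,500 patients give at least 500 per class only about half the time, and a floor of 630 needs about 630 ÷ (1/3) = 1,890 patients.

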cMRI	cardiac magnetic resonance imaging

KEYWORDS

- COVID-19
- Heart failure
- Ejection fraction
- Machine learning

STUDY SUMMARY

TITLE DUO-EF-19: Diagnosis of Heart Failure in the Post-COVID-19 Clinic, Primary Care and Hospital Setting Using a Digital Stethoscope with AI ECG

DESIGN Prospective cross-sectional study

AIMS

1. To validate detection of left ventricular ejection fraction (LVEF) above or below 40% using single-lead ECG interpreted by machine learning algorithm (DUO-EF) compared to gold-standard investigations for calculating LVEF (echocardiography [echo], and a subgroup in cardiac MRI [cMRI])
2. To conduct a real-world evaluation of DUO-EF detection of LVEF above or below 40% in the primary care and COVID-19 follow up clinic setting; validated against subsequent gold standard investigations
3. To evaluate the positive and negative-predictive value of DUO-EF at 24 months

Methods

1. Head-to-head comparison of DUO-EF against gold standard investigation (echo and cMRI) for classifying LVEF<40%; in unselected patients attending for routine echocardiography (main study group) and cardiac MRI (subgroup) as part of their routine clinical care
2. Point-of-care DUO-EF in patients where GP suspects new heart failure and comparison with:
 - a. Subsequent DUO-EF at time of gold-standard investigation (if indicated as standard of care)
 - b. Ejection fraction as calculated by gold-standard investigation
3. Point-of-care DUO-EF in patients attending COVID-19 follow up clinic where clinician suspects new heart failure and comparison with:
 - a. Subsequent DUO-EF at time of gold-standard investigation for HF
 - b. Ejection fraction as calculated by gold-standard investigation

Telephone call follow-up at 24 months for all patients with DUO-EF suggestive of HFrEF but normal gold standard investigations

**OUTCOME
MEASURES**

- **1.) Primary: Sensitivity and specificity of DUO-EF for detecting LVEF above or below 40%**
- 2.) Secondary:
 - DUO-EF performance against subgroup LVEF calculated by cardiac MRI
 - Consistency of DUO-EF result at point-of-care in GP practice ('real world' use where GP suspects new heart failure) against repeat DUO-EF at time of gold-standard investigation
 - Consistency of DUO-EF result at point-of-care in Covid-19 follow up clinic ('real world' use where clinician suspects new heart failure) against repeat DUO-EF at time of gold-standard investigation

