3.1 STUDY OUTCOME MEASURES

The study will end after 36 months or at the point where the predetermined number of participants have been recruited; and 24-month follow up phone call has been completed for those with DUO-EF suggestive of LVEF<40% but gold-standard LVEF >40%.

Primary outcome measure:

- **Sensitivity, specificity for DUO-EF detecting LVEF above or below 40%**

Secondary outcome measures:

- DUO-EF performance against subgroup %LVEF calculated by cardiac MRI
- Consistency of DUO-EF result at point-of-care in GP practice ('real world' use where GP suspects new heart failure) against repeat DUO-EF at time of gold-standard investigation; similarly with patients attending Covid-19 follow up clinic with symptoms of LVEF <40%
- Development of LVEF <40% at 24 months in participants with initial DUO-EF suggestive of LVEF <40% but gold standard investigations LVEF >40% i.e. can DUO-EF predict future development of LVEF <40%
- DUO-EF point-of-care determination of LVEF<40% in comparison with the components of the established NICE pathway (BNP result)

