6. ASSESSMENT AND FOLLOW-UP

Please see table below describing follow up procedures for different groups of the study. Describe how incidental findings will be identified, reviewed and reported, and to which individuals they will be reported to (i.e. GP, clinical care team).

	Group 1: All-comers to echo/cardiac MRI	Group 2: GP patients	Group 3: COVID-19 follow-up clinic
Follow-up	Follow-up phone call at 24 months for all patients with positive DUO-EF but negative gold standard investigations for LVEF <40% (to evaluate if positive DUO-EF is an indicator of future risk for developing LVEF <40%)		

The recruitment for the study will end when the requisite number of participants has been achieved. For some groups, there will be a long-term follow up period as described above. The study will end upon completion of these follow up periods.

In those patients where a 24 month follow up phone call is indicated, we will first attempt to confirm whether or not the participant is deceased by review of the NHS Spine, thereby avoiding unnecessary distress for relatives.

Incidental Findings

Incidental findings are highly unlikely in the course of this study since the process of having DUO-EF would not identify anything additional to what would be found during standard of care. In the unlikely event of the study team making an incidental finding they will notify the team in charge of the patient's care at the time-of-appointment.

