7. STATISTICS, DATA ANALYSIS, DATA SECURITY

Data Analysis

Data will be analysed using a statistical package and platform (R Studio). Analysis will be completed by a clinical research fellow with appropriate access privileges (including honorary Imperial NHS contract) to study data.

Data Protection, Security and Compliance

This study has been reviewed and approved by the Imperial College Healthcare NHS Trust Data Protection Office (reference 20HH6360). Data and all appropriate documentation will be stored for a minimum of 10 years after the completion of the study, including the follow-up period.

All study data will be collected using a REDCap (Research Electronic Data Capture) database, with a unique study ID for each participant (only identifiable by the principal investigator using an encrypted master key held in a password protected file on NHS servers). Patients will be allocated a de-identified study ID number, derived from a key that processes NHS numbers algorithmically. This key will be kept secure in a password encrypted file (accessible only to principal investigator). Study participant data will therefore not be identifiable unless researchers revert study ID's to NHS number.

The following data (where available) will be captured by researchers from the electronic health record (EHR):

- Encrypted NHS number (master key held in password protected file on NHS server, only accessible to principal investigator)
- Age
- Ethnicity
- Comorbidities
- Classification into study group 1-3
- BNP blood test result
- Echocardiography calculated %LVEF and categorisation
- Cardiac MRI calculated EF and categorisation

Eko DUO Data Security

The only data received by Eko Health will be digital ECG data. This will not be identifiable to the patient (i.e. not associated with an NHS number, date of birth or other identifier and Eko will not have access to the key for linkage with NHS numbers). This digital ECG data is uploaded to the Eko cloud via the mobile phone app (connected to the Eko DUO by bluetooth, no data stored on the device).

The data can be freely retrieved and will only be accessed through and securely stored within Imperial College London computers and servers. At the end of the study, all digital ECG data will be retrieved from Eko's servers and stored in accordance with Imperial College London policy on secure College computers.

No ECG or other data is stored on the mobile phone/on the app.

Interim Analysis

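### The statement that the design precludes confounders does not hold for the 24-month objective, where borderline baseline LVEF can be counted as DUO-EF prediction

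*Protocol*

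**What the plan says.** In section 3 of the Protocol, among the notes to the sample size calculation, one line reads in full: "Confounders: our study design precludes confounders". The dropout note in the same block is expressly restricted to the primary objective, and the bias subsection that follows is restricted by its title. This line carries no restriction.

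Section 2 sets a prognostic secondary objective: whether participants with a positive DUO-EF but a gold-standard LVEF above 40% "are at increased risk of developing heart failure at 24 months i.e. can DUO-EF predict future development of LVEF <40% at 24 months". Section 3.1 makes the outcome "Development of LVEF <40% at 24 months in participants with initial DUO-EF suggestive of LVEF <40% but gold standard investigations LVEF >40" per cent.

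Section 6 defines who is followed and how: "Follow-up phone call at 24 months for all patients with positive DUO-EF but negative gold standard investigations for LVEF <40" per cent. Section 3 (Group 1) and Appendix 1 agree. No repeat echocardiogram is scheduled, and no DUO-EF-negative participant is followed. The Study Summary words the followed set differently: "Telephone call follow-up at 24 months for all patients with DUO-EF suggestive of HFrEF but normal gold standard investigations".

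Section 3 records LVEF as a value and in three classes: low (40% or less), moderately depressed (41-49%) and normal (50% or more). The value may come from 3-D echo, from a biplane or M-mode method, or from a visual estimate. A reported range is replaced by its midpoint.

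**The concern.** The 24-month objective is an observational claim about an exposure (a positive DUO-EF) and a later outcome (LVEF below 40%), and nothing in the design removes confounding from it. DUO-EF is an LVEF classifier, so among people above 40% it is plausibly positive more often in those just above the line. The same people are the most likely to have a later value below 40%, through a small decline or through measurement error alone.

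Because entry and outcome use the same 40% cut, someone read at 43% and later at 38% counts as having developed the outcome even if the heart has not changed. Under the objective's wording that event supports the statement that DUO-EF foresees low LVEF. At stake is the trial's only prognostic claim, which could look favourable for an algorithm that merely detects current borderline function.

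**Working it through.** **1. The plan's own figures.** The 24-month objective has no stated event rate, effect size or power, so there is no figure of its own to reproduce. The primary figure of 466 per LVEF class does reproduce: an exact one-sample binomial test of 80% against 85%, upper-tail alpha 0.025, first reaches 80% power at n = 466 (80.5%). With the planned 500 participants above 40%, the number followed would be 500 × (1 − specificity): 500 × 0.15 = 75 at 85% specificity, or 500 × 0.20 = 100 at 80%.

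**2. Does baseline LVEF link to both sides?**
- To DUO-EF: section 1.1 reports an AUC of 0.841 (0.754 to 0.906) for EF below 50% in 100 patients. This fits an output that tracks LVEF around and above 40%. The class also contains LVEF below 40%, so it supports the link without proving it.
- To the outcome: with one cut-off for entry and outcome, closeness to 40% at baseline raises the chance of a later value below it.

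**3. Illustration with no true change (all inputs assumed).** True LVEF T is half N(32, 8) and half N(58, 8). P(DUO-EF positive | T) = 1/(1 + exp((T − c)/8)), with c set so that sensitivity equals specificity, at about 80%. Two readings are taken of the same T, each with independent error N(0, s). The quantity is P(second reading < 40 | DUO-EF positive, first reading > 40).

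| s (points) | all followed (>40%) | baseline ≥50% only | share of conversions from baseline <50% |
|---|---|---|---|
| 3 | 15% | about 0.1% | almost 100% |
| 5 | 24% | about 3% | about 95% |
| 7 | 32% | about 10% | about 86% |

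Of 100 people followed, 15 to 32 would appear to convert although nobody's LVEF had changed, if all were re-measured.

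**4. A second illustration, with real decline that depends on baseline class only.** Let m be the share of the above-40% group in 41-49%, a and b the DUO-EF-positive rates in 41-49% and ≥50%, and r1 and r2 the 24-month risks in those classes. The conversion proportion among positives is [m·a·r1 + (1−m)·b·r2] / [m·a + (1−m)·b]. With m = 0.2, a = 0.4, b = 0.1, r1 = 0.15, r2 = 0.02:
- numerator: 0.0120 + 0.0016 = 0.0136
- denominator: 0.08 + 0.08 = 0.16
- proportion: 0.0136/0.16 = 8.5%, against 2% in the ≥50% class
- share from 41-49%: 0.0120/0.0136 = 88%

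Over m = 0.1-0.3, a = 0.3-0.5, b = 0.10-0.15 and r1 = 0.10-0.20, with r2 = 0.02, the proportion runs from 3.5% to 14.3%, and the 41-49% class supplies 53% to 96% of conversions. DUO-EF adds nothing beyond baseline class in any of these cases.

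**5. What handling of baseline LVEF can achieve.** Suppose DUO-EF negatives were also followed and re-measured. In the model of step 3 about 3%, 5% and 7% of them would convert, a spurious risk ratio of about 5. Restricting to baseline ≥50% still leaves a ratio of about 4-5. Adjusting for the measured baseline value leaves an odds ratio of about 1.6-2.9, because that value carries the same error. Restriction and adjustment therefore reduce the false signal without removing it.

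**The case against.** The line sits in a block about the primary objective. For a paired comparison of an index test with a reference standard, confounding is largely beside the point, so the authors may have meant no more than that. This is fair as to intent. As written, though, the line is unrestricted while its neighbours are restricted, and it is untrue for an objective in the same protocol.

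A reader might infer that the protocol forgoes adjustment because of this sentence. The documents do not show that. No 24-month analysis method is stated, an SAP may exist, and baseline LVEF, age and comorbidities are all captured. The point rests on a wrong statement and on how the outcome is defined; it does not rest on a missing analysis detail. Nor does anything in the documents show that a further covariate is needed.

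A reader might also infer that the trial would report a spurious relative risk of about 5. It could not, because no DUO-EF negatives are followed.

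The telephone-only follow-up also stands as an objection to the size. LVEF at 24 months is known only where care outside the study measured it, and a person not re-measured cannot cross 40% through measurement error. The 15-32% is conditional on re-measurement.

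Finally, if 'normal' in the Study Summary is meant in the protocol's own sense of 50% or more, the 41-49% group is not followed and most of the problem goes. The objectives and the outcome measure say above 40%, so the two wordings must be reconciled.

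**Conclusion.** The concern holds for the 24-month secondary objective only; the primary accuracy comparison is not affected. The unqualified sentence is wrong there, and the shared 40% cut lets borderline or misread baselines count as prediction. The direction follows from the definitions, given that DUO-EF is positive more often near 40%, which is plausible but not reported directly.

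The size is not fixed by the documents. With no true change and everyone re-measured, about 15-32% of those followed would convert, against about 0.1-10% with baseline 50% or more. These figures rest on the assumed LVEF distribution, a measurement SD of 3 to 7 points, and a DUO-EF that depends on true LVEF alone.

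The bias is in a conversion proportion. Separately, increased risk cannot be estimated from DUO-EF positives alone, whatever is done about baseline LVEF. It would also be too strong to infer that restricting to 50% or more, or adjusting for baseline LVEF, would establish prediction: step 5 shows that a false signal would remain.

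**What to change.** 1. Limit the confounders sentence in section 3 to the primary objective.
2. Reconcile the Study Summary's 'normal' with the above-40% wording in the objectives and outcome measures, so that the followed set has one definition.
3. Report 24-month conversions separately for baseline 41-49% and 50% or more, and do not count conversions from 41-49% as evidence of prediction.
4. State the result as a descriptive conversion proportion among those whose LVEF is known at 24 months. Drop the increased-risk wording unless DUO-EF negatives above 40% are ascertained in the same way.
5. If such a contrast is made, stratify or adjust for baseline LVEF, and say that measurement error leaves residual confounding.

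Items 1 to 4 need wording changes and a tabulation by classes already recorded. A comparison group would add follow-up work and is needed only if the risk claim is kept. The cost is fewer events and a weaker prognostic claim.
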